8.1 Definitions

Unanticipated Problems Involving Risk to Subjects or Others

Any incident, experience, or outcome that meets all of the following criteria:

- Unexpected in nature, severity, or frequency (i.e. not described in study-related documents such as the IRB-approved protocol or consent form, the investigators brochure, etc.)
- Related or possibly related to participation in the research (i.e. possibly related means there is a reasonable possibility that the incident experience, or outcome may have been caused by the procedures involved in the research)
- Suggests that the research places subjects or others at greater risk of harm (including physical, psychological, economic, or social harm).

Adverse Event

An **adverse event** (AE) is any symptom, sign, illness or experience that develops or worsens in severity during the course of the study. Intercurrent illnesses or injuries should be regarded as adverse events. Abnormal results of diagnostic procedures are considered to be adverse events if the abnormality:

- results in study withdrawal
- is associated with a serious adverse event
- is associated with clinical signs or symptoms
- leads to additional treatment or to further diagnostic tests
- is considered by the investigator to be of clinical significance

Serious Adverse Event

Adverse events are classified as serious or non-serious. A **serious adverse event** is any AE that is:

- fatal
- life-threatening
- requires or prolongs hospital stay
- results in persistent or significant disability or incapacity
- a congenital anomaly or birth defect
- an important medical event

Important medical events are those that may not be immediately life threatening, but are clearly of major clinical significance. They may jeopardize the subject, and may require intervention to prevent one of the other serious outcomes noted above. For example, drug overdose or abuse, a seizure that did not result in in-patient hospitalization, or intensive treatment of bronchospasm in an emergency department would typically be considered serious.

All adverse events that do not meet any of the criteria for serious should be regarded as **non-serious adverse events**.

Adverse Event Reporting Period

The study period during which adverse events must be reported is normally defined as the period from the initiation of any study procedures to the end of the study treatment follow-up. For this study, the study treatment follow-up is defined as 30 days following the last administration of study treatment. After 30 days, only adverse events related to an increase in seizure frequency or symptoms of depression will be reported.

Preexisting Condition

A preexisting condition is one that is present at the start of the study. A preexisting condition should be recorded as an adverse event if the frequency, intensity, or the character of the condition worsens during the study period.

General Physical Examination Findings

At screening, any clinically significant abnormality should be recorded as a preexisting condition. At the end of the study, any new clinically significant findings/abnormalities that meet the definition of an adverse event must also be recorded and documented as an adverse event.

Post-study Adverse Event

All unresolved adverse events should be followed by the investigator until the events are resolved, the subject is lost to follow-up, or the adverse event is otherwise explained. At the last scheduled visit, the investigator should instruct each subject to report any subsequent event(s) that the subject, or the subject's personal physician, believes might reasonably be related to participation in this study.

Abnormal Laboratory Values

A clinical laboratory abnormality should be documented as an adverse event if any one of the following conditions is met:

- The laboratory abnormality is not otherwise refuted by a repeat test to confirm the abnormality
- The abnormality suggests a disease and/or organ toxicity
- The abnormality is of a degree that requires active management; e.g. further diagnostic investigation, etc.

Hospitalization, Prolonged Hospitalization or Surgery

Any adverse event that results in hospitalization or prolonged hospitalization should be documented and reported as a serious adverse event unless specifically instructed otherwise in this protocol. Any condition responsible for surgery should be documented as an adverse event if the condition meets the criteria for an adverse event.

Neither the condition, hospitalization, prolonged hospitalization, nor surgery are reported as an adverse event in the following circumstances:

- Hospitalization or prolonged hospitalization for diagnostic or elective surgical procedures for a preexisting condition. Surgery should **not** be reported as an outcome of an adverse event if the purpose of the surgery was elective or diagnostic and the outcome was uneventful.
- Hospitalization or prolonged hospitalization required to allow efficacy measurement for the study.
- Hospitalization or prolonged hospitalization for therapy of the target disease of the study, unless it is a worsening or increase in frequency of hospital admissions as judged by the clinical investigator.

8.2 Notification and Recording of Self Harm as Indicated by the MINI and/or QIDS

Subjects will complete a series of assessments several times during their participation in the study. Two of the assessments, the MINI and the QIDS, are validated measures of depression. On the QIDS, participants are asked to select a response that best describes how they have been feeling in the past seven days. Item 12 asks about "Thoughts of Death or Suicide." This particular question will be reviewed by study personnel each time the subject completes the QIDS. Each time a subject responds positively to this question by selecting a 2 ("I think of suicide or death several times a week for several minutes.") or a 3 ("I think of suicide or death several times a day in some detail, or I have made specific plans for suicide or have actually tried to take my life.") the following procedure will be followed by study personnel:

- 1) Administer the Columbia Suicide Severity Rating Scale (C-SSRS).
- 2) Notify the study psychiatrist and an appropriate clinician (if needed) for assessment.
- 3) In REDcap, under **Safety Reporting**, document that the subject gave this answer, when the answer was given, and the clinician(s) notified.
- 4) The notified clinician may follow up with the subject and take appropriate action according to the unique situation. If the answer is given after exposure to TMS, treatment may be discontinued or reduced.

The MINI contains a module that asks subjects about suicidal ideation and behavior in the past month. The six items in this module have a possible point total of 33. A score above 6 corresponds to a "Moderate" current risk of suicide, while a score of 10 or above indicates a "High" current suicide risk. In cases where a subject reports a score of 6 or greater, the above procedure will be followed by study personnel.

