8.4 Recording of Adverse Events

At each contact with the subject, the investigator must seek information on adverse events by specific questioning and, as appropriate, by examination. Information on all adverse events should be recorded immediately in the source document, and also in the appropriate adverse event module of the case report form (CRF). All clearly related signs, symptoms, and abnormal diagnostic procedures results should be recorded in the source document, though should be grouped under one diagnosis.

All adverse events occurring during the study period must be recorded. The clinical course of each event should be followed until resolution, stabilization, or until it has been determined that the study treatment or participation is not the cause. Serious adverse events that are still ongoing at the end of the study period

must be followed up to determine the final outcome. Any serious adverse event that occurs after the study period and is considered to be possibly related to the study treatment or study participation should be recorded and reported immediately.

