8.5.1 Investigator reporting: notifying the Dartmouth IRB

This section describes the requirements for safety reporting by investigators who are Dartmouth faculty, affiliated with a Dartmouth research site, or otherwise responsible for safety reporting to the Dartmouth IRB. The Dartmouth College IRB (CPHS) requires expedited reporting of those events related to study participation that are unforeseen and indicate that participants or others are at increased risk of harm. The Dartmouth IRB will not acknowledge safety reports or bulk adverse event submissions that do not meet the criteria outlined below. The Dartmouth IRB requires researchers to submit reports of the following problems within 10 working days from the time the investigator becomes aware of the event:

- Any adverse event (regardless of whether the event is serious or non-serious, on-site or off-site) that occurs any time during or after the research study, which in the opinion of the principal investigator is:

Unexpected (An event is “unexpected” when its specificity and severity are not accurately reflected in the protocol-related documents, such as the IRB-approved research protocol, any applicable investigator brochure, and the current IRB-approved informed consent document and other relevant sources of information, such as product labeling and package inserts.)

AND

Related to the research procedures (An event is “related to the research procedures” if in the opinion of the principal investigator or sponsor, the event was more likely than not to be caused by the research procedures.)

Reporting Process

Unanticipated problems posing risks to subjects or others as noted above will be reported to the Dartmouth IRB using the form: “Unanticipated Problems Posing Risks to Subjects or Others Including Reportable Adverse Events” or as a written report of the event (including a description of the event with information regarding its fulfillment of the above criteria, follow-up/resolution and need for revision to consent form and/or other study documentation).

Copies of each report and documentation of IRB notification and receipt will be kept in the Clinical Investigator’s study file.

Reporting Deaths: more rapid reporting requirements

Concerning deaths that occur during the course of a research study, the following describes the more rapid reporting requirement of the Dartmouth IRB for specific situations:

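### Section 8.1 limits reporting after day 30 to seizure- and depression-related events, which contradicts 8.4 and 8.5.1 and could leave some late related serious events unreported

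*Combined protocol and SAP*

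**What the plan says.** Three parts of the safety section govern what happens to an adverse event that arises late.

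- **Section 8.1, Adverse Event Reporting Period.** The period in which events must be reported "is normally defined as the period from the initiation of any study procedures to the end of the study treatment follow-up". It continues: "For this study, the study treatment follow-up is defined as 30 days following the last administration of study treatment". The restriction follows: "After 30 days, only adverse events related to an increase in seizure frequency or symptoms of depression will be reported".
- **Section 8.4.** The late events it covers are these: "Any serious adverse event that occurs after the study period and is considered to be possibly related to the study treatment or study participation". The action it asks for is that such an event "should be recorded and reported immediately". The type of event does not matter. The section also says: "At each contact with the subject, the investigator must seek information on adverse events by specific questioning and, as appropriate, by examination".
- **Section 8.5.1.** The IRB must be told within 10 working days of any adverse event, serious or not, "that occurs any time during or after the research study", if the principal investigator judges it both unexpected and related. Related here means more likely than not caused by the research procedures. Deaths during the study have their own deadlines of 24 or 72 hours.

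Follow-up continues well past day 30. The SAFTEE is given at Visit 8 (3 months) and Visit 9 (6 months), and the MoCA and RBANS at Visit 9 (Sections 6.9 and 6.10).

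**The concern.** Section 8.1 defines an SAE as a kind of adverse event, so the word *only* in the reporting-period paragraph takes in SAEs as well. Neither 8.1 nor 8.4 refers to the other. A coordinator who learns at Visit 8 or 9 of a possibly related SAE outside the two named categories finds one section that excludes it from reporting and another that demands an immediate report.

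Safety is the first aim of this study. Hypothesis 1.a treats hospitalization as well as seizure increase as serious. Stopping rule 2c in Section 8.7 counts patients with significant TMS side effects other than seizures and states no time limit. Recruitment was planned within a study running from November 2015 to October 2020, so a late event in an early participant can matter for later ones. The documents do not say which records feed the stopping-rule count, so an effect on that rule is possible but cannot be shown.

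**Working it through.** The plan gives no figure to reproduce on this point. The check compares the rules, then does simple calendar arithmetic.

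**Step 1: do the rules cover the same time?** Under 8.1's own definition the study period ends at day 30 after the last TMS. The period that 8.4 describes as after the study period therefore starts where the 8.1 restriction starts. If 8.4 instead meant the whole six months, the conflict would not go away, because 8.4 also requires every adverse event within the study period to be recorded.

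**Step 2: what does each rule require?** Take an event after day 30 that concerns neither seizures nor depression, with the study period ending at day 30.

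| Late event | 8.1 restriction | 8.4 | 8.5.1 |
|---|---|---|---|
| Non-fatal SAE, unexpected, more likely than not related | excluded | report | report |
| Non-fatal SAE, possibly but not more likely than not related | excluded | report | not covered |
| Non-fatal SAE, related but expected | excluded | report | not covered |
| Non-serious, unexpected and related | excluded | not covered | report |
| Death during the study | excluded | report if possibly related | report in 24 or 72 hours |
| Non-serious, expected | excluded | not covered | not covered |

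The first four rows conflict, and so does the row on deaths. In the second and third rows 8.4 is the only rule requiring a report, so that is where following 8.1 literally does most damage. The last row is no contradiction: limiting late routine reporting to named categories is a choice open to the sponsor.

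**Step 3: how much of follow-up is affected?** Inputs are the day-30 cutoff (8.1) and Visit 9 at 6 months plus or minus 4 weeks after Visit 5 (6.10). Assumptions: the last TMS is given at Visit 5, and a month is 30 to 30.44 days.

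- Share under the narrow rule = (follow-up days − 30) / follow-up days.
- Nominal Visit 9, about day 183: (183 − 30) / 183 = 153/183 = 0.84. Full reporting covers 30/183 = 0.16.
- Earliest Visit 9, 180 − 28 = day 152: 122/152 = 0.80.
- Latest Visit 9, about 183 + 28 = day 211: 181/211 = 0.86.
- Visit 8 falls at about day 62 to 119, so Visits 8 and 9 are always past the cutoff. Visit 7 (1 month plus or minus 2 weeks, about day 16 to 44) can fall on either side.

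**The case against.** The strongest reply is that the sections can be read together: 8.1 limits routine reporting after day 30, and 8.4 is the specific provision for SAEs after the study period. On that reading a possibly related SAE is reported. The monitoring plan (Attachment E) may also settle the matter, but it is not available here. The reading is workable, but the text does not state it. There is no cross-reference. Section 8.1 also says that hospitalizations are reported as SAEs unless the protocol instructs otherwise, and the *only* sentence could be taken as such an instruction.

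The second reply is that there are safety nets, and this stands in part. Section 8.5.1 still sends unexpected, more-likely-than-not related events to the IRB at any time, and deaths during the study are covered. Section 8.1 asks participants at the last visit to report later events they believe may be related. A reader might infer that late harm would simply be absent from the trial's safety record or never reach the IRB. The documents do not support that. The SAFTEE, MoCA, RBANS and enquiry at each contact all continue after day 30, and many serious surprises would go to the IRB under 8.5.1.

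A reader might also try to express the problem as a shift in the SAE proportion and its exact confidence limit in Section 7. That does not fit. Section 7.1 defines the analysed SAEs as seizures or hospitalizations, so a late non-hospitalized event outside those categories would not enter the numerator under any reporting rule.

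**Conclusion.** The contradiction is real. Section 8.1 on one side and 8.4 and 8.5.1 on the other give incompatible instructions for the same months, and the passages must be reconciled. The consequence is a possibility, not a certainty: it arises if staff apply the 8.1 sentence as written.

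The main exposure is narrow: a non-fatal SAE after day 30 that concerns neither seizures nor depression and is either expected or judged possibly but not more likely than not related. The restriction covers about 84% of nominal follow-up (80% to 86% across the Visit 9 window). That is a share of calendar time. The documents give no rate of late events, so it says nothing about how many reports would be lost. The conclusion assumes that the unseen monitoring plan does not already resolve the conflict. A correction is worth making because it costs little and removes a written rule that could suppress a safety report in a study whose first aim is safety.

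**What to change.** Reconcile 8.1 with 8.4 and 8.5.1 by rewording the restriction, for example:

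*After 30 days, routine adverse event reporting is limited to events related to more frequent seizures or to depressive symptoms; this does not limit the reporting of serious adverse events possibly related to study treatment or participation (8.4) or of events reportable to the IRB (8.5.1).*

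Both cross-references are needed. Adding only possibly related SAEs would still shut out the unexpected, related, non-serious events that 8.5.1 requires to be reported. If the monitoring plan repeats the restriction, align it at the same time.

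The cost is one sentence and perhaps a few more reports. The contacts and measures that would bring these events to light are already scheduled.

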4.2.1 When and How to Discontinue Treatment

Treatment will be discontinued and the subject may be withdrawn from the study prior to completion due to any of the following reasons:

1. The subject experiences greater than 3 typical seizures during the 3 day course of TMS treatment or they experience a single atypical seizure (atypical duration or severity for the patient) as judged by study neurologist.
2. The subject experiences a worsening of depressive symptoms by the discretion of the study psychiatrist.
3. The subject withdraws consent.
4. The subject is not able to tolerate TMS (as assessed by self-reported side effects).
5. The subject does not adhere to protocol requirements.

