6.1 Visit 1a: Initial Screening by Neurologist – Pre-enrollment

- Patient will review and sign informed consent.
- Initial screening will be done by a board-certified neurologist (, Visit 1a). Patient's history and physical will be taken, medications will be reviewed, seizure log, MOCA will be performed if time permits. All incomplete assessments may be done at Visit 1b.
- Subject will receive seizure log and instructions for its use.

6.2 *Visit 1b: Initial Screening by Psychiatrist – Pre-enrollment*

- Subsequent evaluation will be done by board-certified psychiatrist and research assistant Visit 1b). If the subject is unable to complete the full screening during Visit 1a, he or she may be scheduled for a second screening appointment with study psychiatrist and research assistant. At that time, diagnosis of medication-resistant depression will be confirmed; the MINI, QIDS, SAFTEE, PANAS MRI safety, TASS and ATHF will be performed. Seizure log data will be obtained.
- If time permits, Visit 2 procedures can be done at Visit 1b.

6.3 *Visit 2: Imaging and Baseline Neuropsychological Testing – Pre Enrollment*

- Patient will be report to the Advanced Imaging Center for MRI. MRI will last approximately one hour.
- After MRI is complete, patient will be brought to the EEG lab . A dense-array EEG will be conducted which will take approximately one hour.
- Patient will do neuropsychological and social-cognition testing, which will last approximately 2 hours. (QOLIE-31, RBANS and MAC-S)
- If time permits, TMS motor threshold may be done at Visit 2, so long as TMS treatment is scheduled to begin within one week. Otherwise, TMS motor threshold will be done at Visit 3.

6.4 *Visit 3: Enrollment and first day of TMS treatment*

- Patient will be brought to DHMC by their proxy for the first day of TMS treatment.
- Research staff will administer the QIDS, SAFTEE, and PANAS. Data will be obtained from the patient's seizure log.

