- Patient will be given TMS motor threshold test to calibrate the machine for treatment, if not done at Visit 2. Following calibration, the designated TMS trained study team member or study RN will begin administering the first TMS treatment session under supervision of the study psychiatrist . Each treatment session will last approximately 50 minutes, and the patient will be given the opportunity to take a break between sessions. The patient will be scheduled to receive four, and may receive as many as seven, treatment sessions by the end of Visit 3.
- Following the final TMS session, study personnel will administer the SAFTEE, and PANAS.
- Following TMS, the family member/proxy will be instructed how to monitor the patient for safety, and he or she will be given contact information in case of unusually strong seizures. A hotel room will have been booked by study personnel prior to the study visit, if needed. The proxy will stay in the same room as the patient between all treatment days.
- The study Neurologist will be on call in case of unusual seizures.
-

6.5 *Visit 4: Second day of treatment*

- The proxy will bring the patient back to DHMC, and report to the Psychiatry Clinic for Visit 4.
- Research staff will administer the SAFTEE and PANAS. Seizure log will be reviewed.
- After completing assessments, the subject will begin the planned seven treatment sessions. Break times will be provided between sessions if desired.
- At the end of the final treatment session, research staff will:
 - Administer the SAFTEE and PANAS.
 - Remind the patient and proxy about contact and safety information before they depart.
- The study Neurologist will remain on call in case of unusually strong seizures.

6.6 *Visit 5: Third day of treatment*

- The proxy will bring the patient back to the Psychiatry Clinic for Visit 5.
- Research staff will administer the SAFTEE, PANAS. Seizure log will be reviewed.
- The patient will have four planned treatment sessions, but may receive as many as seven treatment sessions, with the opportunity to rest between trains.
- Once the final TMS treatment session is complete, a second dense-array EEG test will be conducted, which will last approximately one hour.
- After completion of the dense-array EEG, research staff will:
 - Administer the SAFTEE, PANAS, QIDS, and MoCA.
 - Debrief patient and proxy. Provide with safety information.
- Patient will be taken home by proxy*.

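### On the planned three-day course, the suicidality answers that Section 8.2 would act on are not scheduled at any contact between the first and last TMS train

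*Combined protocol and SAP*

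**What the plan says.** Section 8.2 names two suicidality triggers: a response of 2 or 3 on QIDS item 12, and a score of 6 or more on the MINI suicidality module. Item 12 is looked at only when a QIDS is filled in: "This particular question will be reviewed by study personnel each time the subject completes the QIDS". A trigger leads to the C-SSRS, notification of the study psychiatrist, documentation, and possible clinical follow-up. On treatment, the section adds: "If the answer is given after exposure to TMS, treatment may be discontinued or reduced".

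The visit lists in Section 6 place the instruments as follows.

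- Visit 1b, screening: "the MINI, QIDS, SAFTEE, PANAS MRI safety, TASS and ATHF will be performed".
- Visit 3, before the first train: "Research staff will administer the QIDS, SAFTEE, and PANAS". After the day's last session, SAFTEE and PANAS only.
- Visit 4, before the trains: "Research staff will administer the SAFTEE and PANAS. Seizure log will be reviewed". After them, SAFTEE and PANAS again.
- Visit 5, before the trains: SAFTEE and PANAS. After the final session and the second EEG: "Administer the SAFTEE, PANAS, QIDS, and MoCA".
- Visits 6 to 9, follow-up: QIDS at each.

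Section 5.1 plans four trains on day 1, seven on day 2 and four on day 3. Sections 5.1 and 6.6 allow a fourth day for patients who have not finished all fifteen.

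**The concern.** A clause about changing treatment in response to an answer given after exposure presupposes that an answer is obtained while some treatment is left. On the three-day plan, the visit lists do not provide for one.

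The population makes the trigger plausible. Section 4.1 excludes item 12 scores above 2 and MINI suicidality scores above 16. Patients who already meet an 8.2 trigger at screening can therefore enter. Section 8.2 covers ideation present at screening or at the Visit 3 QIDS, because the C-SSRS and psychiatrist notification would come before the first train. Ideation that appears or worsens during the course is what lacks a scheduled screen. In a trial whose main purpose is safety, a stated safety provision should have the data it needs at the time it is meant to apply.

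**Working it through.** No sample size, power or error-rate figure bears on this point. The check sets the visit lists in Section 6 against the train plan in Section 5.1 and counts.

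**Planned trains:** 4 + 7 + 4 = 15.

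**Contacts from the start of Visit 3 to the end of Visit 5, with planned trains still to come:**

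| Contact | Trains given | Trains left | QIDS | MINI |
|---|---|---|---|---|
| Visit 3, start | 0 | 15 | yes | no |
| Visit 3, end | 4 | 15 − 4 = 11 | no | no |
| Visit 4, start | 4 | 11 | no | no |
| Visit 4, end | 4 + 7 = 11 | 15 − 11 = 4 | no | no |
| Visit 5, start | 11 | 4 | no | no |
| Visit 5, end (after EEG) | 15 | 0 | yes | no |

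**Result.** Four contacts fall after the first planned train and before the last. QIDS is scheduled at 0 of 4 and MINI at 0 of 4. All 15 planned trains lie between two consecutive QIDS administrations. The first scheduled item 12 answer after treatment begins arrives with 0 planned trains left.

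**Fourth day.** If the final session mentioned in Section 6.6 means the last of that day, the Visit 5 QIDS comes before any day-4 trains and the clause could act on those. If it means the last of the whole course, the QIDS still follows every train. The text does not settle this, and it lists no assessments for a fourth day.

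**Motor threshold.** Section 6.3 allows threshold testing at Visit 2, so the Visit 3 QIDS may follow a few test pulses. It still precedes all 15 treatment trains. The count above takes exposure to mean treatment trains.

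**Recall period.** According to Section 8.2, QIDS respondents choose what "best describes how they have been feeling in the past seven days". That window is longer than the three-day course, and response 2 on item 12 is worded in terms of frequency per week. This may explain why the QIDS is not repeated daily. It does not supply the answer that Section 8.2 relies on.

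**The case against.** The strongest reply is that Section 8.2 is permissive, promises no mid-course QIDS, and is not the only safeguard. Most of that stands.

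- Section 4.2.1 separately allows treatment to be discontinued when "The subject experiences a worsening of depressive symptoms by the discretion of the study psychiatrist", and sessions run under the study psychiatrist's supervision.
- Section 8.4 requires specific questioning about adverse events at each contact, and Section 8.1 counts a pre-existing condition that worsens as an adverse event. Information is therefore solicited at all four contacts and does not depend on the patient volunteering it.
- SAFTEE and PANAS are given at all four contacts, and Section 3.3 says the PANAS has been validated against measures that include depression.

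These routes keep the gap from being a complete absence of protection. They do not close it. None is tied to a scheduled suicidality item, Section 8.2 does not use SAFTEE or PANAS as a trigger, and the documents do not say whether the SAFTEE asks about suicidal thoughts.

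Two stronger readings are tempting, and the documents do not support them. A reader might infer that nothing could change treatment for emergent ideation before the last train; Sections 4.2.1 and 8.4, and possibly the fourth day, rule that out. A reader might also infer that the worsening-depression criterion in 4.2.1 lacks a score it needs. The QIDS is scheduled on day 1 and again on day 3, and that criterion rests on the psychiatrist's judgement, not on a score.

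**Conclusion.** The point holds in limited form. On the planned three-day course, neither trigger in Section 8.2 is scheduled at any of the four contacts between the first and last train, so the treatment-change clause has no scheduled input until no planned train remains. This is a mismatch between a safety provision and its schedule. It does not show that patients are unmonitored.

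The conclusion assumes that the Section 6 visit lists are complete and that treatment follows the 4 + 7 + 4 plan. Table 1 (cited in Section 3.3) and Attachments B, C and E (visit guide, procedures table, monitoring plan) were not in the text available. If they already schedule a screen during treatment, the correction needed is to Section 6. For patients who use the fourth day, the point is open until the meaning of the final session in 6.6 is clarified.

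**What to change.** Reconcile Section 8.2 with Sections 6.4 to 6.6, and with any fourth day, so that the suicidality screen 8.2 relies on is collected at existing contacts while treatment is still in progress. The sponsor should choose an instrument and recall period suitable for repeat use over days. Simply shortening the recall of item 12 to the interval since the last visit would not work well, because one triggering response is worded per week. Section 6.6 should state whether the Visit 5 assessments come before or after any fourth-day trains. What action follows a positive answer is for the sponsor to decide.

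The cost is a few minutes of assessment at contacts where staff already administer scales, and an amendment to the visit lists. With 20 patients, a screen at all four contacts adds at most 4 × 20 = 80 short administrations. One at the start of Visits 4 and 5 only adds 2 × 20 = 40. Under the procedure as written, each positive answer would also bring a C-SSRS and a psychiatrist notification. No extra visit is needed.
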